1.5 Sample Size Justification

The effects of PTBT on the outcomes of interest are unclear given that there are no prior data. However, our studies of differences in puff topography in the context of acute stress vs. control produce medium-sized effects ($ds=0.46-0.54$).³⁶ Thus, we believe a medium size effect is clinically meaningful, and therefore, the sample size was calculated to detect a medium effect size difference across training groups. **Mean Difference.** For linear regression models, a sample size of 58 is sufficient to detect a medium effect size ($f^2=.143$ [R^2 change/1-cumulative R^2] = .143) with 80% power and alpha of 0.05 via multiple regression analyses with up to 10% variance explained by the main predictor (training group) and up to 5 other covariates (e.g., sex, number of cigarettes per day, depressive/anxiety symptom severity, corresponding baseline values, and CO boost) accounting for up to additional 20% of the anticipated variance. Without any covariates in the model, a sample size of 73 is needed to detect a medium effect size ($f^2=.11$) across training groups (explaining 10% variance). **Mediation (Aim 3).** Statistical power for a mediation analysis with a single mediator was estimated using Monte Carlo power analysis for indirect effects.⁸⁶ The inclusion of mediation analyses led us to increase our sample size to $n=80$, which is sufficient for detection of indirect effects with a proportion-mediated effect size of 50%⁸⁷ (correlations between predictor, mediators, and outcome, $r=.40-.43$) with 80% power and alpha of 0.05. which we deemed sufficient given the exploratory nature of these analyses. **Taken together**, to ensure analyses are adequately powered, we propose a sample of 88 (allowing for ~8-10% attrition) with a final intended sample of 80 completers (40 per condition).

[figure not shown]

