Test of Aim 1: First, tests of the effects of puff training on puff topography indices (i.e., puff volumes and duration, and inter-puff intervals) will be conducted using linear regression models. The mean level of each index over the course of the stress-precipitated smoking session will be calculated for each individual to be used as outcomes. The primary independent variable is training group (PTBT vs. Control). Planned covariates include biological sex (0=male, 1=female), number of cigarettes per day, and emotional distress (DASS-21), and the models will be tested with and without covariates. Effect size (d) will also be calculated. In addition, a series of multilevel models will be used to test whether 1) the mean levels and 2) changes in the levels of puff topography (i.e., volume, duration, inter-puff intervals) during stress-precipitated smoking session differ across groups. Levels of puff volumes, durations, and inter-puff intervals for each puff (outcomes), and puff number (level 1) make up the first level of data nested within individuals at the second level. Training group and other baseline characteristics will be entered in the models as level 2 variables. We will examine the effects of PTBT (vs. Control) on the individual mean (i.e., the middle point of the values over time) and the individual trajectory slope (i.e., the rates of changes over time) for each topography index in separate models. A cross-level interaction term between training group (level 2) and puff number (level 1) will be included in each model. Puff number will be centered around the mid-point for each individual so that the intercept reflects the estimated mean level of each topography outcome. Separate quadratic and cubic slopes (squared and cubic puff number) will be included as level 1 predictors if their inclusion improves model fit. Intercepts and slopes will be specified as random if it improves model fit and coefficients varied significantly across individuals. Deviance statistics will be used to compare model fit between two models.⁷⁹ Unconditional models will be initially estimated, and then training group will be included as a level-2 variable predicting level-1 intercept and slope coefficients. The models will be fitted with and without level 2 planned covariates (i.e., sex, FTCD, DASS-21, and the baseline average value of the corresponding outcome).

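### Making the random puff-number slope conditional on significance can modestly understate the standard error of the group-by-puff-number test

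*Combined protocol and SAP*

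**What the plan says.** Section 6.1 (Test of Aim 1) first regresses each person's mean puff volume, puff duration and inter-puff interval on training group. It then adds multilevel models with puffs nested in persons, in which "A cross-level interaction term between training group (level 2) and puff number (level 1) will be included in each model". The random part is chosen from the data: "Intercepts and slopes will be specified as random if it improves model fit and coefficients varied significantly across individuals". On how fit is judged, it says "Deviance statistics will be used to compare model fit between two models", with no significance level, degrees of freedom or reference distribution. On sequence, "Unconditional models will be initially estimated, and then training group will be included as a level-2 variable". On coding, "Puff number will be centered around the mid-point for each individual".

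Nothing in the document commits to a random slope for the term being tested. It names no robust standard error, small-sample degrees of freedom or sensitivity model for the case where the slope is fixed. Section 1.5 sizes the study for the linear regressions and the mediation analysis and gives no figure for the trajectory test.

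**The concern.** Training group varies between persons, so a group difference in slopes must be judged against how much slopes differ between persons within a group. Fixing the slope takes that component out of the error term. A non-significant variance test in 80 people does not show that the variance is zero, and the rule sets two conditions before the slope may be random. Where real variation is missed, the interaction is tested against a standard error that is too small, and false trajectory differences become more frequent than the nominal 5%.

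Trajectory is one of the two topography summaries listed as outcomes in section 1.3, and section 1.4 presents puff-to-puff analysis as an advance on averages. The three trajectory tests should therefore have a sound error term.

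**Working it through.** **Plan's own figures.** With f² = .143, six predictors and N = 58, the noncentrality is .143 × 58 = 8.29 on 1 and 51 df, and power is 0.807. With f² = .10/.90 = .111 and one predictor, N = 73 gives 80% power. For "allowing for ~8-10% attrition", 80/(1 − 0.09) = 87.9, so 88. All three reproduce, but they concern the regressions on means and say nothing about the trajectory test.

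**Inputs.** From section 1.5: N = 80 (40 per arm) and alpha 0.05, taken as two-sided. Assumed, because the document gives no figure: K puffs per person (8 to 15; 8 to 20 in the unequal case), the slope variance, and the retention cut. A random intercept is taken as retained.

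**Formulas.** Let σ² be the puff-level residual variance, τ the between-person slope variance, and Sxx = (K³ − K)/12. The ratio r = τ·Sxx/σ² compares slope variance with the sampling variance of one person's slope. Centring within person separates the slope part from the intercept part.

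- True variance of the interaction: 4σ²(1 + r)/(N·Sxx)
- Variance used when the slope is fixed: about 4σ²[1 + r/(K − 1)]/(N·Sxx)

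The second is smaller whenever r > 0 and K > 2. For K = 15 and r = 0.3, the ratio of standard errors is √[(1 + 0.3/14)/1.3] = √(1.0214/1.3) = 0.89. In concrete terms, Sxx = (3375 − 15)/12 = 280, so one standard deviation of slope is √(0.3/280) = 0.033 residual SD per puff. That is 14 × 0.033 = 0.46 residual SD from first to last puff.

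**How often the slope is missed.** Simulation without a group effect, K = 15, REML deviance test on 2 df at 0.05 in the unconditional model, 200,000 trials per setting:

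| r | slope missed | model SE / true SE | type I error when missed |
|---|---|---|---|
| 0.1 | 97% | 0.96 | 5.9% |
| 0.2 | 90% | 0.92 | 6.7% |
| 0.3 | 78% | 0.89 | 7.3% |
| 0.4 | 63% | 0.86 | 7.8% |
| 0.5 | 47% | 0.83 | 8.3% |

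**Overall type I error.** Missed and retained trials together, equal puff counts, peak over r:

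| retention test | peak |
|---|---|
| 2-df deviance test | about 6.9% |
| 1:2-df mixture | about 6.7% |
| AIC-type cut (deviance drop over 4) | 6.1 to 6.3% |
| 1-df boundary test | 5.8% |

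At r = 0 the rule holds 5%. At r = 1.0 under the 2-df test it gives about 5.1 to 5.3%, because only 3 to 6% of trials still miss the slope. Always keeping the slope gives 4.1 to 5.1%, the low end being at r = 0.

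**Unequal puff counts.** With 8 to 20 puffs, the 2-df test and 4,000 trials per setting (simulation error about ±0.7 points), the rule gives 6.5 to 7.5% for r from 0.1 to 0.6. Always keeping the slope gives 4.5 to 5.8% across the settings run. At the 7.5% peak (r = 0.3), always keeping it gave 5.8%, so the excess there is 1.7 points.

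**The case against.** The rule limits its own harm. It drops the slope mainly when slope variance is small, which is when the standard error is least wrong. The excess lies in a band between zero and large variance, and nothing in the document shows that this trial falls in it. The size also turns on a retention test that the plan leaves open; under a 1-df boundary test the excess is below 1 point. Aim 1's directional hypotheses concern average volume, average duration and inter-puff intervals. They are tested first, by regression on person means, and the multilevel models are additional. Fit-based selection of random effects is a recognised parsimony choice, and always keeping the slope has its own cost in power.

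All of this stands as a limit on size and scope. It does not remove the point: parsimony is not neutral when the component dropped is part of the error term of the tested effect, and no other section restores it.

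Several stronger readings are tempting but not supported:

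- **Puffs treated as independent.** A retained random intercept still models clustering within person; only slope differences are left out.
- **Error rates of 10 to 24%.** These belong to a model that never fits a random slope when r is 0.5 to 2. Under the stated rule, slope variance at the upper end of that range is nearly always detected.
- **A 19% chance of some false trajectory finding.** 1 − (1 − 0.069)³ = 19% assumes three independent indices, all at the worst-case variance. Volume and duration of the same puff are unlikely to be independent, and 1 − 0.95³ = 14% is ordinary multiplicity, a separate matter.

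**Conclusion.** The concern holds as a minor one. If slope variance is small to moderate (r about 0.2 to 0.5), the planned rule often misses it, and the trajectory test runs at about 6 to 7% instead of 5%: 5.8 to 6.9% by retention test with equal puff counts, and about 7.5% with unequal counts. Among equal-count trials where the 2-df test drops the slope at r of 0.3 to 0.4, the error is about 7 to 8%. It is near 5% when slope variance is zero or large.

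These figures rest on the assumed puff counts, slope variance and retention cut. A reader might infer that false trajectory findings will exceed 5% whatever the data look like, or that the main Aim 1 results are compromised. The document supports neither. It gives no slope variance, and the rule does not touch the regressions on person means or Aims 2 and 3.

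**What to change.** State in section 6.1 that every Aim 1 multilevel model testing group by puff number includes a random intercept and a random linear puff-number slope, whatever their significance, with Satterthwaite or Kenward-Roger degrees of freedom. Allow simplification only if the model does not converge, and then use person-cluster-robust standard errors for the interaction. Keep the fit-based rule for random quadratic and cubic terms.

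This is a change of a sentence or two, and it puts all three indices on the same error term. If slope variance is truly zero, the cost is about 1 to 3 points of power (from 80% to between 77% and 79%) and a slightly conservative test, at about 4.2%.

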1.3 Research Design and Methods

This study is an experimental, between-subjects test of biofeedback puff topography training (relative to sham training) in reducing stress-induced smoking reinforcement. Specifically, combustible cigarettes smokers ($n = 80$) will be randomized to receive puff topography biofeedback ($n = 40$) or sham training ($n = 40$) prior to exposure to a laboratory stressor paradigm. Stress-precipitated smoking behavior will be assessed directly after the stressor task, wherein participants will be given the instructions to smoke utilizing their assigned puff training. Smoking reinforcement will be measured using a multi-method approach, including self-report, psychophysiology, and behavioral indices (see Measures). Outcome variables include: (1) puff topography indices (averages, trajectory) and (2) reinforcer pathology indices (delay reward discounting, cigarette demand, urges, affect, and smoking enjoyment).

A. Research Procedures

See **Figure 3** for an overview of the experimental procedures. Participants will complete a telephone interview to verify key exclusion/inclusion criteria. Participants who appear to be eligible will be scheduled for a remote assessment session. If eligible following the remote session, participants will be scheduled for two in-person visits on consecutive days. For standardization (internal validity), all in-person visits will be scheduled to occur ~4hrs following the estimated time of participants' first cigarette of the day. Participants will be informed that they will smoke their second daily cigarette during the lab visit and instructed to avoid behaviors that may confound CVC (e.g., vigorous physical activity or consumption of caffeine within 2 hr; alcohol use within 12 hr).

Baseline Assessment (Remote Visit): Staff will obtain written informed consent, after which participants will complete an eligibility assessment (see **Table 1**). They will then complete the baseline assessment battery (see **Table 1**).

[figure not shown]
Training Visit (V1): Participants will be screened for final eligibility criteria (e.g., CO level) upon arrival. Assessment of self-reported affective and smoking related variables will be conducted via self-report at various times throughout the session (see the orange stars on **Figure 3**).

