Participants will be attached to physiological recording equipment throughout the session, including blood pressure volume, ECG, and respiration. When they smoke (in a ventilated smoking room), smoking topographical indices will be recorded using the handheld *Clinical Research Support System* (CReSS micro; described in **C.7**).

Training Conditions: Eligible participants will then be **randomized** to either the PTBT or Control (Sham Training) and informed that the training will be used in V2. **Block randomization** will be used with biological sex (female vs. male) as a blocking variable, as sex is a known factors that influences puff topography and reinforcement.^{36,58,59} Both trainings will be time-matched.

PTBT: PTBT is designed to decrease puff topography influences on smoking reward informed by heart rate variability biofeedback paradigms. Participants will be taught how to puff in a way that may feel different from their usual puffing behavior. Participants will be hooked up to a respiratory band, electrocardiogram (ECG) electrodes, and a blood volume sensor finger cuff (pulse plethysmograph) while seated in a ventilated smoking room. Following a 5-min adaptation period, they will be introduced to a breathing pacer (EZ-Air Plus; Biofeedback Foundation of Europe), which is integrated with the *Thought Technology* biofeedback interface (**Figure 4**), and taught how to use the pacer to guide the pace of their inhalation and exhalation. Participants will be taught to breathe steadily as a white ball (pacer) proceeds up the incline, and exhale as they follow the ball on the decline. They will first practice breathing normally with the pacer to ensure they understand the procedures. Then, participants will smoke following the pacer while using the CReSS micro device for a 5-min phase. To address reinforcement immediacy and intensity, the pacer will be set to a 2 sec inhalation matched with a 2 sec exhalation, for a 4 sec cycle, such that *puffing* maps onto a respiration pace of 15 breathes/min. **This pace should minimize CVC (Figure 2, right).** To address reinforcement reliability, the inter-puff-interval will vary between 4 secs and 30 secs as the experimenter will instruct the participant when to puff. In an adjacent room, the experimenter will be able to monitor real-time displays of physiological data and observe the session via video

Figure 4. Example of Biofeedback Display during PTBT

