conferencing system and provide additional training instructions, as needed. Participants will then complete a 5-min rest period.

Control: In the control condition, i.e. sham training, participants will be hooked up to the same physiological monitoring equipment and complete the same 5-min adaptation period. They will then be instructed to smoking with the CreSS device while focusing their attention during a 5-min vanilla task.⁶⁶ The task involves attending to a computer screen and counting the number of times a designated color rectangle occupies the screen. Different colored rectangles are presented one at a time, for 500ms every 10 sec, for a total of 5-min. The full color spectrum is reflected and participants are told to make their best guess about color match. Participants are asked at the end to report the number of times the designated color was observed and are not given any feedback or incentive for correct color counts. No instructions will be provided about puffing behavior. Participants will then complete a 5-min rest period.

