1.6 Study Variables

A. Independent Variables, Interventions, or Predictor Variables

1. Training Conditions: Eligible participants will then be **randomized** to either the **Puff Topography Biofeedback (PTBT)** or **Control (Sham Training)** and informed that the training will be used in V2. Block randomization will be used with biological sex (female vs. male) as a blocking variable, as sex is a known factors that influences puff topography and reinforcement.^{36,58,59} Both trainings will be time matched.

PTBT: PTBT is designed to decrease puff topography influences on smoking reward informed by heart rate variability biofeedback paradigms. Participants will be taught how to puff in a way that may feel different from their usual puffing behavior. Participants will be hooked up to a respiratory band, electrocardiogram (ECG) electrodes, and a blood volume sensor finger cuff (pulse plethysmograph) while seated in a ventilated smoking room. Following a 5-min adaptation period, they will be introduced to a breathing pacer (EZ-Air Plus; Biofeedback Foundation of Europe), which is integrated with the *Thought Technology* biofeedback interface (**Figure 4**), and taught how to use the pacer to guide the pace of their inhalation and exhalation.

Figure 4. Example of Biofeedback Display during PTBT

Participants will be taught to breathe steadily as a white ball (pacer) proceeds up the incline, and exhale as they follow the ball on the decline. They will first practice breathing normally with the pacer to ensure they understand the procedures. Then, participants will smoke following the pacer while using the CreSS micro device for a 5-min phase. To address reinforcement immediacy and intensity, the pacer will be set to a 2 sec inhalation matched with a 2 sec exhalation, for a 4 sec cycle, such that *puffing* maps onto a respiration pace of 15 breathes/min. This pace should minimize CVC (**Figure 2, right**). To address reinforcement reliability, the inter-puff-interval will vary between 10 secs and 30 secs, as the experimenter will instruct the participant when to puff. In an adjacent room, the experimenter will be able to monitor real-time displays of physiological data and observe the session via video and intercom system and provide additional training instructions, as needed. Participants will then complete a 5-min rest period.

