1.9 Data Collection

A. Primary Data Collection

- **Location:** This project will be conducted at the Rutgers University Affective and Biological Underpinnings of Substance Use and Anxiety (ABUSA) Laboratory located on the 2nd floor of [name]. The lab space is equipped with two rooms for psychophysiological assessment with adjacent rooms for monitoring, an in-lab smoking room that is ventilated to the outdoors with an adjacent control room for monitoring. Some eligibility and baseline assessments will be conducted remotely, using video-conferencing software (e.g., HIPAA compliant Zoom or Teams platforms) and online survey collection software (e.g., Qualtrics).
- **Process of Data Collection:** Data will be collected by IRB-approved and trained research staff from both labs of the Principal Investigators, in accordance with the procedures described in detail in section 1.3. In brief, combustible cigarettes smokers with emotional distress (N=88) will be randomized to receive puff topography biofeedback (n = 44, 50%) or sham training (n = 44, 50%) prior to exposure to a laboratory stressor paradigm. Stress-precipitated smoking behavior will be assessed directly after the stressor task, wherein participants will be given the instructions to smoke utilizing their assigned puff training. Smoking reinforcement will be measured using a multi-method approach, including self-report, psychophysiology, and behavioral indices
- **Timing and Frequency:** After the initial telephone screening, data collection will occur on one remote occasion and two in-person occasions. The remote session entails one initial assessment to confirm eligibility and collection of baseline data via interview and self-report. For the in-person visits, V1 entails data collection through self-report measures (administered at the starred time points in **Figure 3**), as well as receiving their assigned training condition. V2 will occur on the following day at the same time as V1.
- **Procedures for Audio/Visual Recording:** The diagnostic interview during the remote session will be recorded via HIPAA compliant platform (e.g., Zoom, Teams) to be used for supervision purposes as well as to ensure diagnostic fidelity.
- **Study Instruments:** **Puff topography** will be objectively measured with the *CreSS micro* (Plowshare Technologies, Borgwaldt KC, Inc), a hand-held device that has a sterilized flow meter mouthpiece that is

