6.0 Data Management Plan

6.1 Data Analysis

Interventional Research Protocol Template (HRP-503a) 2.4.20

PI: [name].; [name].

Protocol Title: Puff Topography Biofeedback on Smoking

Reinforcement

Protocol Version Date: 2020000645 v.21 05/02/2023

Prior to conducting outcome analyses, we will use descriptive statistics and graphical analysis to evaluate the distributional properties of outcome variables. T-tests and χ^2 initial analysis will be used to evaluate the equivalence of the groups on baseline variables (i.e., successful randomization).

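### The adjusted Aim 1 multilevel models use a baseline topography covariate with no named occasion, and the only pre-V2 topography the text describes is the V1 training cigarette, smoked after randomization

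*Combined protocol and SAP*

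**What the plan says.** Section 6.1 tests Aim 1 in two ways.

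- **Linear regressions** on each person's mean puff volume, duration and inter-puff interval at V2. The planned covariates are sex, cigarettes per day and DASS-21.
- **Multilevel models** of puff-level data, fitted with and without level-2 covariates: "i.e., sex, FTCD, DASS-21, and the baseline average value of the corresponding outcome". The occasion of the baseline value is not stated.

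The rest of the protocol describes the following about topography before V2.

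- **Remote session (1.9):** "collection of baseline data via interview and self-report". No topography device is mentioned.
- **V1 (1.9):** "V1 entails data collection through self-report measures", plus delivery of the assigned training.
- **Lab cigarettes (1.3):** participants are told that "they will smoke their second daily cigarette during the lab visit".
- **Order at V1 (1.3):** final eligibility check, randomization, then smoking within the assigned condition. For PTBT: "Then, participants will smoke following the pacer while using the CReSS micro device for a 5-min phase". For Control: "They will then be instructed to smoking with the CreSS device while focusing their attention during a 5-min vanilla task".
- **Cueing (1.6):** in PTBT the inter-puff interval is varied, "as the experimenter will instruct the participant when to puff". Control participants get no puffing instructions.
- **Table 1 (1.9):** the CReSS row carries one mark, which reads as the Smoking column.

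By contrast, section 1.9 does name the reference occasion for RSA: the V1 adaptation period.

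**The concern.** A baseline covariate improves precision safely only if assignment cannot have changed it. Here the one earlier topography value the text describes is taken while one arm is paced and cued and the other is counting colored rectangles. PTBT acts directly on that value, and for inter-puff interval the experimenter sets it.

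An analyst who follows 6.1 and looks for a topography value before V2 would find that cigarette. Adjusting for it removes from the group coefficient the part of the V2 difference already visible at V1. What is left is the V2 difference beyond what V1 puffing predicts, which is not the training effect stated in Aim 1. The adjusted and unadjusted multilevel fits would then sit side by side, and a gap between them could be read as a matter of precision when it is bias.

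**Working it through.** **1. The plan's own figures (section 1.5).** With covariates, f² = 0.10/(1 − 0.30) = 0.143. A noncentral F test with one tested predictor among six, alpha 0.05, gives N = 58 (power 0.807). Without covariates, f² = 0.10/0.90 = 0.111 gives N = 73 (power 0.802). Both match the plan. For attrition, 80/(1 − 0.09) = 87.9, so 88, which also matches. The sample size is not in dispute.

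**2. Effect on the d scale.** Ten percent of variance with equal arms is d = 2·√(0.10/0.90) = 0.667. A two-sample t test with 40 per arm has power 0.84.

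**3. Effect of adjusting for V1.** Use analysis of covariance on person means as a stand-in for the multilevel mean-level coefficient, with unit within-arm SD at both visits and effects signed in the hypothesized direction:

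- expected adjusted coefficient = d(V2) − b·d(V1), where b is the within-arm slope of V2 on V1 (b = r when the SDs are equal);
- standard error = √(1 − r²) · √[(2/40)·(1 + d(V1)²/4)].

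Worked case, r = 0.5 and d(V1) = d(V2) = 0.667:

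- coefficient = 0.667 − 0.5·0.667 = 0.333;
- standard error = 0.866·√(0.05·1.111) = 0.204;
- ratio 1.63, power 0.36.

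**4. Range.** Neither r nor d(V1) is in the documents; section 1.5 says there are no prior data on PTBT. Both are assumptions. Power is from 20,000 simulated trials per cell; where the closed form above applies, it agrees to within about 0.015.

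| V1 shift | Adjusted d at r = 0.3 / 0.5 / 0.7 | Power |
|---|---|---|
| None, or a value the training cannot have changed | 0.67 / 0.67 / 0.67 | 0.87 / 0.92 / 0.98 |
| Half the V2 effect | 0.57 / 0.50 / 0.43 | 0.73 / 0.70 / 0.74 |
| Equal to the V2 effect | 0.47 / 0.33 / 0.20 | 0.53 / 0.36 / 0.22 |
| Equal, with r = 0 in PTBT (cued puffs) and r as shown in Control only | 0.57 / 0.50 / 0.43 | 0.67 / 0.57 / 0.49 |

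In the equal-shift row, 30%, 50% and 70% of the effect is removed.

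**5. The null case.** With no V2 effect but a V1 shift of 0.667, the adjusted coefficient is −0.20, −0.33 or −0.47 at r = 0.3, 0.5 or 0.7. The closed form gives rejection in 14%, 36% and 78% of trials.

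**6. Reach.** The Aim 1 linear regressions list no baseline topography, so they are not exposed. Nor are the unadjusted multilevel fits. The group-by-puff-number slope is exposed only if the covariate is also allowed to predict the slope.

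**The case against.** The strongest reply is that a pre-training value is probably what the authors mean. The opening of 6.1 uses baseline variables to judge whether randomization succeeded, which makes sense only for values assignment cannot have changed.

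The evidence of absence is also imperfect. The visit summary in 1.9 is not exhaustive: for V1 it omits the CO, ECG and topography recording that 1.3 describes. Table 1 does not separate V1 from V2. Section 1.3 says topography is recorded when participants smoke, before it reaches randomization. Figure 3, to which the reader is sent for time points, is not available. All of this stands, and it makes the harm conditional. It does not supply an occasion, and no sentence describes a separate pre-training cigarette.

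The reply is also right that reach is narrow, that r and the V1 shift are assumed, and that person-mean covariance analysis without sex, FTCD and DASS-21 only approximates the specified model.

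A last fair point concerns the remedy. Requiring a value from before randomization would be too strict. Sections 1.3 and 1.6 describe the V1 adaptation period after randomization, yet a measurement there can precede any training. The condition that matters is that the value precedes training and is unaffected by assignment.

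**Conclusion.** The gap is real, and its severity is minor to moderate. On the described schedule, the only value available to fill the covariate is one that PTBT directly manipulates. If it is used, the adjusted multilevel mean-level coefficient does not estimate the training effect. The loss runs from nothing (no V1 shift) to 70% of the effect (equal shift, r = 0.7), under an assumed correlation and V1 shift.

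Three stronger readings go beyond the documents.

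- **That the plan adjusts for a post-randomization value.** The text leaves the occasion open, and Figure 3 could show an earlier cigarette.
- **That the Aim 1 result as a whole is compromised.** The linear regressions and unadjusted fits are untouched. Section 1.5 does count corresponding baseline values among the regression covariates, but the Aim 1 regression list in 6.1 leaves them out.
- **That the adjusted effect will reverse sign.** This needs b·d(V1) to exceed d(V2). For example, a V1 shift twice the V2 effect gives 0.667 − 0.7·1.333 = −0.27 at r = 0.7. Nothing in the documents points to a V1 shift of that size.

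**What to change.** In 6.1, under Aim 1, state that the baseline topography covariate is the mean of the index from a named occasion, recorded before any training and unaffected by assignment. If such a value is collected, keep the covariate, since it would raise power above the unadjusted 0.84.

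If no such value is collected, remove it from the level-2 covariates, adjust only for the other planned ones (sex, FTCD, DASS-21), and report V1 training topography descriptively by arm. The choice should be written down before outcome data are analyzed.

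The cost is one or two sentences, with no new data and no change in sample size. The downside is that, without the covariate, the adjusted models may explain somewhat less variance. Unadjusted power at 80 completers remains 0.84 at the plan's effect.
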